7. PROCEDURE PLAN

All EUS/FNB and EUS/FNA will be performed using a linear array echoendoscope by one of seven experienced EUS physicians at JHH. All patients will undergo both EUS/FNB and EUS/FNA. Patients will be randomized to either FNB or FNA first by

means of computer-generated numbers. The endoscopist will not be blinded to the randomization; however, the study pathologist will be blinded to randomization.

EUS/FNB will be performed using similar techniques for tissue acquisition as FNA using 22-g FNB needle (Medtronic SharkCore or Boston Scientific Acquire). Lesions will be identified using EUS and punctured with the 22-g FNB needle (10-15 back and forth movements per needle pass, fanning as appropriate). After the lesion is punctured, the stylet will be removed and 10cc suction will be applied. FNB samples will be placed directly into formalin containers and sent to be processed by surgical pathology.

EUS/FNA with ROSE will be performed using standard techniques via 22-g FNA needle (Cook Medical EchoTip Ultra or Boston Scientific Expect or Medtronic Beacon). Lesions will be identified using EUS and punctured with the FNA needle (10-15 back and forth movements per needle pass, fanning as appropriate). After the lesion is punctured, the stylet will be removed and 10cc suction will be applied. FNA specimens will be processed for ROSE using standard techniques with bedside smear slide evaluation and liquid-based cytology and cell-block preparation.

The first randomization assigned EUS sampling technique will be used until adequate specimen is achieved (up to 3 passes total). After 3 passes, the patient will undergo the other EUS sampling technique until adequate specimen is achieved (up to 3 passes total). If inadequate biopsies are obtained after a total of 6 passes (3 with initial tissue acquisition techniques, 3 with the other technique), the endosonographer will be permitted to utilize any EUS sampling technique preferred to obtain a diagnosis during the same procedure or at a later date.

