12. STATISTICAL CONSIDERATIONS

Overview: This study is designed as a non-inferiority trial.

Considering a success rate of 85% in the FNA with ROSE group, based published studies, we selected a non-inferiority margin (∂) of 10%, in accordance with the USFDA recommendations (8). Based on the following formula (9):

n = f(α, β) × [πs × (100 – πs) + πe × (100 – πe)] / (πs – πe – d)2

where πs and πe are the true percent 'success' in the standard and experimental treatment group respectively, and

 $f(\alpha, \beta) = [\Phi - 1(\alpha) + \Phi - 1(\beta)]2$

 Φ -1 is the cumulative distribution function of a standardized normal deviate

We calculated that our trial will require enrolling 120 patients for power of 80% and two sided α of 0.05.

Taking into consideration a 10% dropout rate, the total patients to be enrolled=132

Baseline demographics, pre-, intra- and post-intervention data will be prospectively collected on data collection forms which will be maintained in an electronic database system. Results will be reported as mean ± standard deviation (SD) for quantitative variables and percentages for categorical variables. The groups will be compared using the Student's t- test or Wilcoxon rank sum test for continuous variables and the chi-square test (or Fisher's exact test if required) for categorical variables. To compare

diagnostic accuracy between two EUS sampling techniques, we will use McNemar's test. Statistical significance will be based on two-sided design-based tests evaluated at α = 0.05. All statistical analyses will be performed using STATA.

a. Endpoints:

Primary:

Diagnostic accuracy will be defined as (true positive + true negative)/all samples. The final diagnosis will be based on one of the following criteria: (i) surgical pathology specimen from patients who underwent surgical resection; (ii) cytological or histopathological diagnosis of malignancy in patients with unresectable disease with appropriate imaging and clinical course of disease; (iii) cytological and histopathological diagnosis of benign disease with an appropriate clinical course of disease for minimum of 6 months.

Secondary:

1. Specimen adequacy

This will be defined as the proportion of samples in which a final histopathological diagnosis could be made.

2. Percentage of histology cores obtained

This will be defined as the proportion of samples in which a visible histology core biopsy was obtained

- 3. Number of passes Number of passes required for diagnosis

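### Secondary endpoint 3 (number of passes) has no value for a technique that gives no diagnosis, so a technique that fails more often can appear to need fewer passes

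*Combined protocol and SAP*

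**What the plan says.** Section 12 (Endpoints, Secondary 3) gives the whole definition: "Number of passes required for diagnosis". The general analysis text in the same section applies to it: "Results will be reported as mean ± standard deviation (SD) for quantitative variables", with a Student's t-test or Wilcoxon rank sum test for continuous variables. Nothing further is said about pass count.

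Section 7 sets the sampling rule: "The first randomization assigned EUS sampling technique will be used until adequate specimen is achieved (up to 3 passes total". The same cap applies to the second technique. The section foresees that both may fail ("If inadequate biopsies are obtained after a total of 6 passes") and then leaves the choice of technique open, without saying what pass count is recorded.

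The two kinds of specimen are handled differently in section 7. For FNA: "FNA specimens will be processed for ROSE using standard techniques with bedside smear slide evaluation and liquid-based cytology and cell-block preparation". For FNB: "FNB samples will be placed directly into formalin containers and sent to be processed by surgical pathology". Neither sentence mentions labelling or reporting by pass. The design is paired: "All patients will undergo both EUS/FNB and EUS/FNA".

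**The concern.** There are two gaps, both in how the endpoint is scored.

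**No value for failures.** A patient in whom a technique gives no diagnosis has no number of passes required for diagnosis with that technique. The plan does not say whether that patient is left out, counted as 3, counted as more than 3, or treated as censored. The literal definition leaves the patient out, which makes the mean conditional on success. The technique with lower yield then loses its hardest patients from its own average.

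**The pass that gave the diagnosis may not be known.** Sampling stops at an adequate specimen, whereas the endpoint refers to a diagnosis. FNA has bedside evaluation during the procedure; FNB has none. If FNB material is not identified by pass, pathology cannot say which pass was first diagnostic, and the recorded figure is the number of passes made.

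Pass count is a natural efficiency result to set beside the aim of dropping on-site evaluation. As the endpoint stands, two analysts could report opposite directions from the same data.

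**Working it through.** The documents give no expected mean, SD or power for this endpoint, so there is no figure of the plan's to reproduce. The check is whether the literal definition can mislead, and under what conditions.

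**Inputs from the documents.** At most 3 passes per technique (section 7); 120 evaluable patients, 85% success with FNA plus ROSE and a 10-point margin (section 12). The 85% refers to the trial's success rate and is borrowed here as a proportion diagnosed. On that basis 0.15 × 120 = 18 patients would lack a diagnosis.

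**Assumed inputs.** All distributions across passes below.

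**Formulas.** Let n1, n2, n3 be the patients first diagnosed at pass 1, 2, 3, and n0 those never diagnosed.
- Diagnosed-only mean = (n1 + 2·n2 + 3·n3) / (n1 + n2 + n3)
- All-patient mean with failures scored k = (n1 + 2·n2 + 3·n3 + k·n0) / 120

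**Worked example.** Technique A: 72/20/10, never 18 (102/120 = 85%). Technique B: 68/16/6, never 30 (90/120 = 75%).

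| | A | B |
|---|---|---|
| Diagnosed by pass 1, 2, 3 | 72, 92, 102 | 68, 84, 90 |
| Diagnosed-only mean | 142/102 = 1.39 | 118/90 = 1.31 |
| Failures scored 3 | (142 + 54)/120 = 1.63 | (118 + 90)/120 = 1.73 |
| Failures scored 4 | (142 + 72)/120 = 1.78 | (118 + 120)/120 = 1.98 |

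B has fewer diagnoses after every pass, yet its diagnosed-only mean is lower. Keeping failures in corrects the order whether they are scored 3 or 4.

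**When the reversal occurs.**
- Mix of lesions (assumed): 75% easy, with yield 0.75 per pass; 25% hard. Lowering the hard-lesion yield per pass from 0.30 to 0.05 cuts the proportion diagnosed from 90.3% to 77.4%. The diagnosed-only mean falls from 1.37 to 1.32, while the mean with failures scored 4 rises from 1.63 to 1.92.
- One constant yield per pass p in all lesions, so that the chance of a first diagnosis at pass j is p(1 − p)^(j−1): p = 0.50 against 0.30 gives 87.5% against 65.7% diagnosed. The diagnosed-only means are 1.57 and 1.77, in the right order. The gap is 0.20, against 0.65 with failures scored 4 (1.88 against 2.53).

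Reversal therefore needs failures concentrated in hard lesions. Without that, the order survives but the difference is understated.

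**Specimen handling.** Bedside smear evaluation gives feedback during FNA sampling, but section 7 does not say that each FNA pass is reported separately, or that the final cytology and cell-block reading is by pass. For FNB it speaks of formalin containers in the plural without tying them to passes. Whether the first diagnostic pass can be recovered for either technique is not settled by the text.

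**The case against.** The strongest reply is that the plan is silent rather than wrong. A reader might infer that failures are dropped, that FNB passes are pooled, or that FNA passes are read one at a time. The documents state none of these. Counting failures as 3 is compatible with the cap, containers could be one per pass, and case report forms that are not in the documents may record the detail. That stands, and it is why the FNB part is put here only as a possibility. It does not remove the first gap, because the stated definition has no value for a patient without a diagnosis.

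A second reply is that the effect is small and visible elsewhere. In the worked example the diagnosed-only SDs are about 0.66 and 0.59 with 102 and 90 patients, so the standard error is about 0.09 and t about 0.9, which is not significant. Specimen adequacy (Secondary 1) would show the lower yield, and primary accuracy is defined over all samples. This also stands: a reader should not infer that the non-inferiority conclusion is at risk. The pass-count result could still point the wrong way, and a separate adequacy figure neither corrects it nor locates the diagnostic pass.

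A third reply is that ranking all failures worst treats a patient stopped after one apparently adequate but non-diagnostic pass like one sampled three times. That is true, and intended: neither obtained a diagnosis under the protocol's stopping rule. The rule should be written down so that the result is read as the technique used under that rule.

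**Conclusion.** The point holds in limited form. Endpoint 3 as defined conditions on success, and no rule covers patients without a diagnosis, although the plan foresees them. A lower-yield technique can appear to need fewer passes: 1.31 against 1.39 in the example, against 1.73 and 1.63 (failures scored 3) or 1.98 and 1.78 (scored 4). The size rests on assumed pass distributions. The reversal requires an analysis confined to diagnosed patients, which the literal wording implies but the plan does not state, and failures concentrated in hard lesions.

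That the FNB count may be passes made rather than passes required is an open question about specimen identification, not an established fault. The consequence is confined to a secondary endpoint; the primary accuracy analysis is not affected.

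**What to change.** - **Endpoint.** Redefine Secondary 3 in section 12 as the cumulative proportion of all sampled patients with a diagnosis by pass 1, 2 and 3, for each technique. Keep patients without a diagnosis in one category ranked worse than three passes, however many passes were made. This costs only wording.
- **Comparison.** Replace the unpaired tests for this endpoint with a paired method, for example Wilcoxon signed-rank on the ordered categories, because every patient receives both techniques. State the score given to the last category. No cost.
- **Specimens.** State in section 7 whether material is identified by pass. If FNB passes are not already kept separate, label containers by pass and have pathology report the first diagnostic pass; say likewise how the diagnostic FNA pass is determined. The cost is at most two extra FNB containers per patient, a line on the pathology report and slightly more processing. It must be settled before sampling, since pooled tissue cannot be separated later.
- **If passes cannot be kept separate.** Call the FNB figure passes made and do not compare it with FNA as passes required.

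None of this alters the sampling rule in section 7.

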13. SAFETY MONITORINGN AND STOPPING RULE

The DSMB will perform a blinded analysis after enrolment and initial outpatient followup of 50% of the study cohort.

Interim analysis will be performed at 50% recruitment. If a > 20% difference in sensitivity is found between both methods then the study will be terminated early

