8. PATIENT FOLLOW-UP

All patients will recover from their procedures according to standard practice. They will remain NPO the night after the procedure. After finishing the procedure, all patients will be carefully monitored per standard protocol in the recovery room and be discharged when fully awake and pain-free. Patients will be contacted by telephone at 24-48 hours to ascertain and document any early adverse events that may have arisen. Long-term clinical follow up will be based on clinical indications.

To determine the safety of procedure, all pre, intra- and immediate post-procedure adverse events will be recorded and rated according to ASGE lexicon (7) for adverse events. Inpatients will be evaluated by study coordinator/PI on a daily basis during their hospitalization. Potential complications will be explained for patients at their discharge time and will be advised to refer whenever they have problems.

- a. Study duration and number of study visits required of research participants. Study duration: 2 years Number of subjects: 132 Follow-up visits: 0
- Blinding, including justification for blinding or not blinding the trial, if applicable.
 Due to the nature of study, treatment team will be aware of patient's group and it is not possible to make it double blinded. However, the study pathologist will be blinded to randomization.

- Justification of why participants will not receive routine care or will have current therapy stopped.
 Routine care will be followed
- d. Justification for inclusion of a placebo or non-treatment group. N/A
- e. Definition of treatment failure or participant removal criteria. The first randomization assigned EUS sampling technique will be used until adequate specimen is achieved (up to 3 passes total). After 3 passes, the patient will undergo the other EUS sampling technique until adequate specimen is achieved (up to 3 passes total). If inadequate biopsies are obtained after a total of 6 passes (3 with initial tissue acquisition techniques, 3 with the other technique), the endosongrapher will be permitted to utilize any EUS sampling technique preferred to obtain a diagnosis during the same procedure or at a later date.
- f. Description of what happens to participants receiving therapy when study ends or if a participant's participation in the study ends prematurely. No change in medical care will be expected.

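### The only stopping rule is an undirected 20% difference in sensitivity, linked neither to the primary endpoint (diagnostic accuracy) nor to its 10-point margin

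*Combined protocol and SAP*

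**What the plan says.** Section 13 sets the timing, "Interim analysis will be performed at 50% recruitment", and then the rule, "If a > 20% difference in sensitivity is found between both methods then the study will be terminated early". It does not say which method must be worse, whether the purpose is futility, efficacy or harm, whether 20% is absolute or relative, or what may be concluded after a stop. The same section adds that "The DSMB will perform a blinded analysis after enrolment and initial outpatient followup of 50% of the study cohort".

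Section 12 states "This study is designed as a non-inferiority trial", and "we selected a non-inferiority margin (∂) of 10" percent. For the primary endpoint, "Diagnostic accuracy will be defined as (true positive + true negative)/all samples". The secondary endpoints are specimen adequacy, histology cores, number of passes, technical failures and adverse events. Sensitivity is in neither list; elsewhere it appears only as a literature range (64–95%) in Section 2.1. Section 7 has every patient sampled by both techniques, with up to three passes each.

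**The concern.** An interim rule should act on the question the trial was built to answer. Here that question is whether FNB without ROSE loses less than 10 points of diagnostic accuracy against FNA with ROSE. The rule uses another measure, has no sign, and carries a threshold with no stated relation to the margin. Two things follow.

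- A large difference in favour of FNB triggers a mandatory stop, and nothing says what that stop means for non-inferiority.
- A deficit that makes a non-inferiority result very unlikely usually does not trigger it. Patients then go on being sampled by both techniques, up to six passes, for a comparison with little chance of success.

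**Working it through.** **The plan's own figure.** Section 12 gives "Considering a success rate of 85% in the FNA with ROSE group", a 10-point margin, 80% power and two-sided α of 0.05, and arrives at 120 (132 with dropout, 120 × 1.10). It does not state the FNB rate. With 85% in both groups its formula gives 7.849 × (85 × 15 + 85 × 15) / 10² = 200.1, so 201 per arm; one-sided 0.05 gives 158. A figure of 120 appears only with unstated inputs: FNB at 90% with one-sided 0.05 (60 per arm), or a paired design with discordance 15.3%, since 7.849 × 0.153 / 0.10² ≈ 120. That is a separate matter. I use 120 only to place the interim at 60 pairs.

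**Assumptions not in the documents.** Discordance is the share of pairs in which exactly one method is right; it must be at least as large as the net deficit. For the stopping rule I take 10–24% among malignant pairs. For conditional power I take 15.3%, 20% and 25.5%, the last being independence at 85% (2 × 0.85 × 0.15). Malignant pairs at the interim: 48 (80% of 60), 53 (80% of 66) and 60 (all of 60). The 20% is read as absolute points.

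**1. How often the current rule stops.** With 53 malignant pairs, 0.20 × 53 = 10.6, so a net count of 11 or more is needed. At a true 10-point deficit with discordance 20%, the expected net is 5.3 and its SD is √[53 × (0.20 − 0.10²)] = 3.17. The normal approximation gives P(net > 10.5) = P(Z > 1.64) ≈ 5%; the exact multinomial value is 5.2%. Exact results over 48, 53 and 60 pairs:

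| True sensitivity deficit of FNB | Probability of stopping |
|---|---|
| 10 points | about 1–8% |
| 15 points (discordance 15–24%) | 11–24% |
| 20 points (discordance 20–24%) | 42–50% |

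Counts are discrete, so the figures move a little with the number of pairs; 54 pairs give about 53% in the last row. By symmetry the same probabilities apply when FNB is better by these amounts. A true 20-point advantage would need FNA sensitivity of 80% or less, which lies within the range quoted in Section 2.1.

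**2. Chance of non-inferiority after a poor first half.** Success at 120 pairs is taken as d − 1.96 × √[(p − d²)/120] > −0.10, where d is the paired accuracy difference (FNB minus FNA) and p the discordance. The final d must then exceed about −3 points (p = 0.153) to −1 point (p = 0.255). After −20 at half-way, the second half must favour FNB by about 14 to 18 points. Exact conditional power:

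| Observed accuracy deficit at 60 pairs | No true difference afterwards | FNB truly 5 points better afterwards |
|---|---|---|
| 10 points (net 6) | 11–22% | 32–59% |
| 12 points (net 7) | 7–14% | 25–47% |
| 13 points (net 8) | 4–7% | 16–31% |
| 15 points (net 9) | 2–4% | 11–22% |
| 20 points (net 12) | 0.1–0.2% | about 2% |

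The current rule fires in none of these rows if the sensitivity gap equals the accuracy gap.

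**3. The two scales.** With equal specificity, accuracy gap = malignant share × sensitivity gap. At assumed shares of 60%, 75% and 90%, a 20-point sensitivity gap is an accuracy gap of 12, 15 or 18 points, in each case beyond the margin.

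**4. A futility rule for comparison.** Stopping at a net 7 or 8 of 60 against FNB would stop about 25–44% of trials at a true 10-point accuracy deficit and 66–81% at 15 (discordance up to 24%). With equal methods it signals in about 0.1–4% of trials and costs about 0.2 points of power or less.

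**The case against.** The strongest reply is that futility is not the plan's stated purpose. The rule stands in a section on safety monitoring, a non-inferiority trial need not have a futility stop, and every patient still receives FNA with ROSE, so continuing denies nobody standard sampling. That is fair: the documents do not show a futility rule that fails. They show a mandatory stop with no stated purpose, no direction and no link to the endpoint, and that criticism stands.

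Four stronger readings are tempting and should not be made.

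- A reader might infer that non-inferiority is already out of reach whenever the rule lets the trial continue. At 10–12 points it is not: conditional power is still 7–22% with no true difference.
- A reader might say that the threshold is twice the margin. That sets an observed half-sample gap in sensitivity against a margin for accuracy at the end; step 3 gives the fair comparison.
- A reader might see a contradiction in a blinded analysis that compares the methods. An unsigned difference can be computed from coded labels, and the DSMB look may be separate from the interim analysis.
- A reader might treat the outpatient follow-up as unscheduled, because Section 8 lists "Follow-up visits: 0". That entry counts study visits; the same section schedules a telephone call at 24–48 hours.

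Two further limits stand. Section 12 names McNemar's test, whereas conditional power here assumes a Wald limit against the margin. The problem also matters mainly if FNB is truly about 10 or more points worse; with equal methods, an observed 15-point deficit at 60 pairs has a probability of only about 0.3–1.5%.

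**Conclusion.** The point holds as a defect in a stated rule, not as missing detail. The stop is mandatory and undirected, and rests on a measure that is not an endpoint. It can end the trial because FNB looks much better, with no defined conclusion. It usually lets the trial continue when FNB is clearly worse: it stops about 1–8% of trials at a true 10-point sensitivity deficit and is roughly a coin toss at 20. Meanwhile an observed 15-point accuracy deficit leaves about a 2–4% chance of success if the methods are equal thereafter.

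The sizes rest on assumed discordance, an assumed malignant share and a Wald criterion. The direction of the finding does not. The final analysis can proceed without the change, so it should be made but is not essential to the trial's validity.

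**What to change.** Replace the sentence in Section 13 with a non-binding futility rule:

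- **Measure and direction.** Use the signed paired difference in diagnostic accuracy (FNB minus FNA), with a possible stop only when FNB is worse.
- **Threshold.** Conditional power below 10%, with its assumption written out, for example equal accuracy of 85% in both methods for the remaining patients. At 60 pairs this is roughly a net 7–8 against FNB; recompute it from the discordance seen and the pairs available. The assumption must be explicit because the plan gives no FNB rate: if FNB were taken as 5 points better, conditional power at a net 7–8 would be 16–47% and the rule would not fire there.
- **Error rate.** No early claim of non-inferiority is made, and the final alpha is unchanged.
- **Data cut.** Run the look on the first 50% of patients once their final diagnoses are available, or report how many pairs have one. Section 12 asks for at least 6 months of clinical course for benign disease, so an immediate cut would tend to leave out recent benign cases.
- **Access.** Only the DSMB sees results by method.

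The DSMB's review of major complications in Section 10.2 is not affected.

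The cost is one paragraph and a closed DSMB report, with the small false-signal rate and power loss shown in step 4. Waiting for diagnoses also shrinks what an early stop can save: if recruitment ran evenly over the 2 years in Section 8, about 75% of patients (18 of 24 months) would be enrolled by the time of the look.
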